## **10.0 SUPPORTIVE CARE AND OTHER CONCOMITANT THERAPY**

In general, concomitant medications and therapies deemed necessary for the supportive care and safety of the patient are allowed, provided their use is documented in the patient records and on the appropriate case report form. Concomitant medication use will be reviewed at each visit to assess for potential interaction with Imatinib. If a medication that has the potential to interact with imatinib is identified at initial screening, the investigator will determine whether it is in the best interest of the subject to continue with participation in the trial. If the potential interaction poses a risk that is deemed unacceptable, the subject will either stop the concomitant medication and wait an appropriate amount of time to allow clearance of this medication prior to taking Imatinib or, if the concomitant medication is unable to be discontinued, then the subject will be excluded from participation in the trial. In the event a subject is prescribed a medication with the potential for interaction with Imatinib during the course of participation in the trial and the potential risk is deemed too high then the subject will be instructed not to start this medication or will have to be withdrawn from study. All subjects will be instructed to discuss any new medications with the investigator or study personnel prior to taking in order to reduce the possibility of serious drug interactions.

**10.1 Investigational Agents:** no other investigational agents may be given while the patient is on study.

### **10.2 Concomitant Medications**

#### **Drugs that may increase imatinib plasma concentrations**

Caution is recommended when administering imatinib with inhibitors of the cytochrome P450 isoenzyme CYP3A4 family (e.g., ketoconazole, itraconazole, erythromycin, and clarithromycin). Substances that inhibit CYP3A4 activity may decrease metabolism and increase imatinib concentrations. There was a significant increase in exposure to imatinib when the compound was co-administered with ketoconazole, a CYP3A4 inhibitor.

#### **Drugs that may decrease imatinib plasma concentrations**

Substances that are inducers of CYP3A4 activity may increase metabolism and decrease imatinib plasma concentrations. Co-medications that induce CYP3A4 (e.g., dexamethasone, phenytoin, carbamazepine, rifampicin, phenobarbital or St. John's Wort) may reduce exposure to imatinib. There was a significant decrease in exposure to imatinib when imatinib was co-administered with rifampicin, an inducer of CYP3A4.

#### **Drugs that may have their plasma concentration altered by imatinib**

Imatinib increases the mean  $C_{max}$  and AUC of simvastatin (a CYP3A4 substrate) 2- and 3.5-fold, respectively, indicating inhibition of CYP3A4 by imatinib. Particular caution is recommended when administering imatinib with CYP3A4/5 substrates with a narrow therapeutic window (e.g., cyclosporine or pimozide). Imatinib will increase plasma concentrations of other CYP3A4 metabolized drugs (e.g., triazolo-benzodiazepines, dihydropyridine calcium channel blockers, certain HMG-CoA reductase inhibitors, etc.).

*In vitro*, imatinib inhibits the activity of cytochrome P450 isoenzyme CYP2D6 at concentrations similar to those that affect CYP3A4/5 activity. Systemic exposure to substrates of CYP2D6 is expected to be increased when co-administered with imatinib. No specific studies have been performed and caution is recommended.

Corticosteroids may induce CYP3A4 and are not routinely recommended on-study unless deemed absolutely necessary. Discussion with the principal investigator is not required prior to initiating corticosteroids.

A list of drugs metabolized by CYP3A4/5 and CYP2D6 is provided in Appendix B.

Concomitant treatment with dysrhythmic drugs, i.e., terfenadine, quinidine, procainamide, sotalol, probucol, bepridil, haloperidol, risperidone, and indapamide, is not recommended.

10.3 Concurrent Anticancer Therapy: Concurrent cancer therapy, including chemotherapy, radiation therapy immunotherapy, or biologic therapy may NOT be administered to patients receiving study drug. If these treatments are administered the patient will be removed from protocol therapy.

## **11.0 EVALUATIONS/MATERIAL AND DATA TO BE ACCESSIONED**

Subjects will be prescreened for potential eligibility prior to initial clinic visit. All entry/eligibility laboratory and imaging studies will be performed at or within 2 weeks of the initial visit. Baseline EKG to rule-out prolonged QTc, and if needed, echocardiogram, is required within 2 weeks of starting protocol therapy. If eligibility studies are drawn but the participant was not able to be enrolled/initiate study drug (e.g. hospitalized) in this timeframe, all eligibility laboratory studies will need to be repeated. EKG and ECHO do not need repeated unless there are new clinical concerns. Each study visit will occur approximately 4 weeks (+/- 1 week) after the previous.

STUDIES TO BE OBTAINED	Baseline	2 Weeks	1 Month	2 Months	3 Months	4 Months	5 Months	6 Months	1 month Off Study
Phone Assessment (Weekly)			X	X					
History	X		X	X	X	X	X	X	X
Physical exam with vital signs	X		X		X			X	X
Height, weight, BSA	X		X	X	X	X	X	X	X
Performance Status	X		X	X		X	X		
CBC/platelet with differential, Reticulocyte Count	X	X	X	X	X	X	X	X	X
HPLC or Hemoglobin EP	X								
Ektacytometry, OxygenScan, F% correlation, Blood Viscosity#	X		X		X			X	X
% ISCs (irreversibly sickled cells)	X		X		X			X	X
D-dimer	X		X		X			X	X
Urine Pregnancy test (female)	X		X		X			X	
CMP^, Mag, Phos, Uric Acid, Amylase, Lipase and tryptase	X		X		X			X	X
Biochemical Analysis Sample	X		X		X			X	X
EKG*	X								X
Echocardiogram*	X								
Patient Pain Journal			X	X	X	X	X	X	X
Concomitant Medication Assessment	X	X	X	X	X	X	X	X	X

**Table 2.** Studies to confirm eligibility and monitor safety and efficacy on imatinib

\*During study treatment, monitor for signs and symptoms of arrhythmia and for edema and fluid retention that may cause congestive heart failure. Obtain EKG/echocardiogram and cardiology consult as clinically indicated.

#Blood samples for these studies to be sent to Cincinnati

[figure not shown]
^CMP should include Albumin, Alkaline phosphatase, ALT (SGPT), AST (SGOT), BUN, Calcium, Chloride, Carbon Dioxide, Creatinine, Glucose, Potassium, Sodium, Total Bilirubin, Total Protein, and a calculation of eGFR.

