### 5.2.2 Exclusion criteria

1. Chronic transfusion protocol.
  - a. Patients currently on a chronic transfusion protocol are not eligible
2. Hydroxyurea Intolerance
  - a. Patients who are ineligible for hydroxyurea due to persistent marrow suppression (e.g. thrombocytopenia, neutropenia)
3. Pregnancy or Breast-Feeding
  - a. Pregnancy tests must be obtained in girls who are post-menarchal. Males or females of reproductive potential may not participate unless they have agreed to use an effective contraceptive method.
4. Concomitant Medications
  - a. Investigational Drugs: Patients who are currently receiving another investigational drug.
  - b. Anti-cancer agents: Patients who are currently receiving other anti-cancer agents.
  - c. The following CYP3A4 inducers are prohibited 14 days before the start of imatinib and during the study with imatinib: rifampin, rifabutin, carbamazepine, Phenobarbital, phenytoin, St. John's wort, efavirenz, and tipranavir.

- d. The following CYP3A4 inhibitors are prohibited 7 days before the start of imatinib and during the study with imatinib: azole antifungals (itraconazole, ketoconazole); clarithromycin, erythromycin, diltiazem, verapamil, HIV protease inhibitors (indinavir, saquinavir, ritonavir, atazanavir, nelfinavir); delavirdine.
- 5. Patients who have an uncontrolled infection.
- 6. Prior use of Imatinib: Patients who have previously received imatinib are not eligible for study.
- 7. Patients who in the opinion of the investigator may not be able to comply with the safety monitoring requirements of the study.
- 8. Patient is < 5 years free of a malignancy. Existence of any other malignant disease is not allowed.
- 9. Patient with Grade III/IV cardiac problems as defined by the New York Heart Association Criteria. (i.e., congestive heart failure, myocardial infarction within 6 months of study).
- 10. Patients with a history of QT prolongation, need for concomitant use of anti-arrhythmics or other agents known to prolong QT interval, or electrolyte derangement that cannot be corrected to within normal limits prior to initiation of study drug.
- 11. Patients with a family history of sudden cardiac death.
- 12. Patient has a severe and/or uncontrolled medical disease other than sickle cell disease (i.e., uncontrolled diabetes, chronic renal disease, or active uncontrolled infection).
- 13. Patient has known chronic liver disease (i.e., chronic active hepatitis, and cirrhosis).

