## **6.0 TREATMENT PROGRAM**

All patients with sickle cell anemia will be treated in the same group. There will not be a randomization.

Patients will receive Imatinib orally once daily for 6 months.

The starting dose for subjects will be 340 mg/m^2/day with a maximum dose of 600 mg daily. Drug doses will be rounded to nearest 50 mg according to the dosing table in Appendix A. Dosing should be based on the body surface area (BSA) obtained at each clinic appointment. Drug will be dispensed as a 30-day supply at each visit. Patients will be asked to bring the prescription bottle with them to each visit to assist with monitoring compliance.

Clinic visits will occur at initiation of imatinib and then every 30 days +/- 7 days. Monthly visits will consist of interim history, assessing for adverse side effects and compliance. Participants will be asked to have blood drawn (see Section 11) 2 weeks +/- 3 days after initiation of the drug. Additionally, during the first two months of drug administration, patients will be called or texted a survey link weekly for follow-up safety assessments, except for the participant's in-clinic visits at week 2, 4 and 8. The survey link will come via an app, called Twilio, that allows REDCap the capability to send SMS text messages to survey respondents. If the patient is unable to be reached by phone for at least 3 of the 4 weekly assessments each month, they will be asked to be seen in clinic for a safety assessment. If the patient is unable to do so, they will be removed from protocol therapy for protocol non-compliance. The 1 month, 3 month, 6 month, and 1-month off-therapy visits will consist of a comprehensive history and physical

exam, as well as laboratory and diagnostic studies documented in Section 10. The other visits (2, 4 and 5-month visits post treatment initiation) will be research-nurse visits, with a provider available to sign the next month's prescription.

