##### **1. Non-hematologic dose-limiting toxicity**

- Any Grade 4 non-hematologic toxicity
- Any Grade 3 non-hematologic toxicity with the specific exception of:
  - Grade 3 ALT that return to levels that meet initial eligibility criteria within 7 days of study drug interruption and that do not recur upon rechallenge with study drug. Note: For the purposes of this trial the ULN for ALT is defined as 45 U/L.
  - Grade 3 AST
  - Grade 3 fever or infection <5 days duration
  - Grade 3 hypophosphatemia, hypokalemia, hypocalcemia or hypomagnesemia responsive to oral supplementation within 14 days of initiating supplementation
  - Asymptomatic Grade 3 elevations in amylase or lipase resolving to <Grade 1 within 7 days of study drug interruption and that do not recur upon re-challenge with study drug
- Grade 2 or greater left ventricular systolic dysfunction OR an absolute decrease in shortening fraction of 8 percentage points from baseline.
- Grade 2 allergic reactions that necessitate discontinuation of study drug will not be considered a dose limiting toxicity.
- Any Grade 2 non-hematological toxicity that persists for  $\geq 7$  days and is considered sufficiently medically significant or sufficiently intolerable by patients that it requires treatment interruption.
- Any adverse event requiring interruption of study drug for  $>7$  days or which recurs upon drug re-challenge.

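### Cheap improvement, not an error: chemistry is scheduled on treatment only at Months 1, 3 and 6, so a symptomless chemistry DLT arising just after Month 3 could wait nominally 84 to 90 days for a scheduled test

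*Combined protocol and SAP*

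**What the plan says.** Table 2, titled "Studies to confirm eligibility and monitor safety and efficacy on imatinib", marks the row "CMP^, Mag, Phos, Uric Acid, Amylase, Lipase and tryptase" at Baseline, Months 1, 3 and 6, and one month off study. It is blank at Week 2 and at Months 2, 4 and 5. The row "CBC/platelet with differential, Reticulocyte Count" is marked in every column. The table's footnote puts ALT, AST, creatinine, bilirubin and the main electrolytes in the CMP.

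Section 6 fits this pattern. Months 1, 3 and 6 are the fuller visits, and "The other visits (2, 4 and 5-month visits post treatment initiation) will be research-nurse visits". It also says: "Drug will be dispensed as a 30-day supply at each visit". Section 6 sets visits 30 days apart (within 7 days either way). Section 11 says: "Each study visit will occur approximately 4 weeks (+/- 1 week) after the previous".

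Section 8 counts as a DLT, when attributable to imatinib, "Any Grade 4 non-hematologic toxicity". It also counts Grade 3 toxicity outside a list of exceptions. Grade 3 ALT, and symptomless Grade 3 amylase or lipase, are excepted only if they resolve within 7 days of stopping drug and do not recur on rechallenge. Section 9 requires drug to be withheld for a non-hematologic DLT, and if it resolves, restarted at 14 days at a lower dose.

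**The concern.** The hold rule in Section 9 can act only on a value that someone has seen. Hematologic DLTs are covered by a CBC at each visit. Rises in ALT, amylase or lipase, and electrolyte shifts, may cause no symptoms, so history, the journal and the safety calls may miss them. The weekly calls also stop after the first two months, and Table 2 marks no physical examination at Months 4 and 5.

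What is at stake is mainly a delayed hold: a patient with a silent chemistry DLT may go on taking imatinib through two further dispensings. A smaller matter is the safety description. Section 15.2 relies partly on counting significant laboratory abnormalities, and for chemistry that count rests on three on-treatment panels.

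**Working it through.** **Inputs.** Visit interval u = 28 days (Section 11) or 30 days (Section 6). Chemistry at visits 0, 1, 3 and 6; CBC at Week 2 and at Months 1 to 6 as well as baseline (Table 2). Planned treatment is 6 months (Section 6). The plan states no figure of its own to reproduce on this point.

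**Number of on-treatment tests.** Chemistry 3 (Months 1, 3, 6); CBC 7 (Week 2 and Months 1 to 6).

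**Nominal gaps, (difference in visit number) × u:**

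| Interval | u = 28 | u = 30 |
|---|---|---|
| Baseline to Month 1 | 28 | 30 |
| Month 1 to Month 3 | 56 | 60 |
| Month 3 to Month 6 | 84 | 90 |
| Longest gap with chemistry also at Months 2, 4 and 5 | 28 | 30 |

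**Effect of the visit windows on Month 3 to Month 6.** If each window runs from the previous visit, the gap is 3 × (u ± 7): 63 to 105 days, or 69 to 111. If windows are fixed to the calendar, it is 3u ± 14: 70 to 98 days, or 76 to 104. So 84 to 90 days is the nominal figure, not the maximum. With monthly chemistry the corresponding maxima are 35 to 37 days (u + 7) and 42 to 44 days (u + 14).

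**Mean wait to the next scheduled panel.** This needs an assumption about when onset occurs, which the documents do not supply. For onset equally likely on each day of a period, mean wait = Σ(L²/2) / (length of period), where L runs over the gaps.

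- Onset anywhere in 6 months, u = 28: (784 + 3136 + 7056)/2/168 = 32.7 days. u = 30: (900 + 3600 + 8100)/2/180 = 35.0 days.
- Onset confined to Months 0 to 3: (u²/2 + 2u²)/(3u) = 0.83u, or 23 to 25 days.
- Onset confined to Months 3 to 6: 3u/2, or 42 to 45 days.
- With monthly chemistry, in all three cases: u/2, or 14 to 15 days.

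**Link to the hold rule.** The first scheduled panel after Month 3 is at Month 6, the end of planned treatment. For an event arising after the Month 3 draw, no scheduled chemistry result exists that could start a Section 9 hold within the planned course.

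**Cost of the change.** 3 panels × 20 patients = 60 panels at most.

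**The case against.** The case for leaving the schedule alone is substantial.

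- *It is a deliberate tiered schedule.* Sections 6 and 11 agree. Section 9 notes hematologic toxicity in CML patients, which may explain the more frequent CBC, and Section 3.2 describes a good safety record. This stands: the plan contains no error here.
- *The event class is narrow and its frequency unknown.* Section 8 excepts Grade 3 AST, Grade 3 ALT, amylase or lipase that resolve and stay resolved, and listed Grade 3 electrolyte falls that respond to oral supplements. This also stands. The figures above are waiting times given that an event occurs; none estimates how many patients are affected.
- *Clinically indicated tests remain possible.* They do, but they need a prompt, and the point concerns events without one.
- *More testing has side effects.* This stands and is counted under the fix.
- *Week 2 also has a CBC draw.* Chemistry could be added there, but the Baseline to Month 1 gap is already 28 to 30 days, so the longest gap would not change.

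A reader might infer that the plan contradicts itself, and the documents do not support that. Section 15.3's promise of continuous DLT monitoring introduces the sequential boundary; it concerns counting DLTs across patients and sets no laboratory frequency. The exclusion for "electrolyte derangement that cannot be corrected to within normal limits prior to initiation of study drug" is a pre-treatment eligibility rule and sets no on-treatment standard. A reader might also infer that the stopping boundary is seriously undermined. It counts patients with full follow-up, so an abnormality that persists to Month 6 can still be found. Only one that resolves between panels is lost, and the documents do not allow that number to be estimated.

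**Conclusion.** The point holds as a low-cost improvement to patient safety, not as a defect in the plan. For a symptomless chemistry DLT arising just after Month 3, the nominal wait for a scheduled test is 84 to 90 days, and scheduled chemistry cannot prompt a hold or dose reduction for it before planned treatment ends.

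The gap lengths follow directly from Table 2 and the two stated visit intervals. The mean waits rest on assumed uniform onset: 33 to 35 days over the whole course, or 23 to 45 days across the early-only and late-only cases, against 14 to 15 with monthly chemistry. How often such an event would occur is unknown from these documents.

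**What to change.** In Table 2, mark CMP, Mag, Phos, Amylase and Lipase at Months 2, 4 and 5, using the blood draws already scheduled for the CBC. Uric acid and tryptase, which Section 8 does not name, need not be added. Dispensing need not wait for the result: a value that meets Section 8 triggers the Section 9 hold once reported. DLT definitions, hold rules and the Section 15.3 boundary stay as they are.

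Costs: at most about 60 extra panels with their laboratory fees, and possibly an extra tube per draw (the documents give no volumes). No visit is added. Some transient abnormalities will be found that the present schedule would miss. Each needs classifying, and some may lead to interruption, or to the 14-day hold with reduction to 260 mg/m². That could slightly raise the DLT count against a boundary built on a rate of 0.2, and slightly reduce exposure before the Month 6 endpoints in a study of 20 patients. The team should accept these effects knowingly when it makes the change.

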### 4.2 Secondary Aims

- 4.21 To assess the effect of imatinib on the frequency of vaso-occlusive pain events in patients with sickle cell disease
- 4.22 To assess the effect of imatinib on the amount of opioid use, frequency of acute chest syndrome, and number of hospitalizations
- 4.23 To assess the tolerability and toxicity of imatinib in patients with sickle cell disease

The clinical outcome will be a secondary aim due to the relatively short duration of the study; we expect to see a reduction in the frequency of vaso-occlusive crises, utilization of opioids, and number of hospitalizations and possibly in the incidence of acute chest syndrome and other SCA-associated complications.

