#### 2. Mechanism of Action

Imatinib (ST1571), a phenylaminopyrimidine derivative, is a selective inhibitor of the tyrosine kinase activity of the *BCR-ABL1* fusion gene (oncoprotein), the product of the Philadelphia chromosome. Imatinib mesylate has also shown high activity in blocking the tyrosine kinase activity of stem-cell factor receptor (SCF), c-kit and platelet-derived growth factor PDGF and cellular events mediated by PDGF and SCF. The ability of imatinib to inhibit *BCR-ABL1* tyrosine kinase activity is related to its occupancy of the kinase pocket of the protein, which blocks access to ATP and prevents substrate phosphorylation inhibiting BCR- ABL dependent cellular proliferation. Imatinib has caused apoptosis or arrest of growth in hematopoietic cells expressing *BCR-ABL1*.

Imatinib is well-absorbed after oral administration; maximum plasma concentrations are achieved 2 to 4 hours after administration. The elimination half-lives of imatinib and its major active metabolite, the N-desmethyl derivative, are approximately 18 and 40 hours, respectively. The elimination half-life of the parent drug in children is approximately 15 hours. Imatinib is approximately 95% protein-bound, mostly to albumin and alpha-1- acid glycoprotein. CYP3A4 is the major enzyme responsible for metabolism. CYP1A2, CYP2D6, CYP2C9, and CYP2C19 play minor roles in metabolism. Drugs metabolized by these same enzymes should be avoided or used with caution to avoid unwanted drug interactions. Severe hepatic impairment (bilirubin >3-10 times ULN) increases AUC by 45% to 55% for imatinib and its active metabolite, respectively. Elimination is predominately in the feces, mostly as metabolites.

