## **14.0 OFF STUDY CRITERIA**

1. Thirty days after the last dose of the investigational agent.
2. Death
3. Lost to follow-up
4. Withdrawal of consent for any further data submission.
5. Enrollment onto another therapeutic study

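### No routine EKG is scheduled while patients take imatinib; the one follow-up tracing comes after washout, so QTc on drug is not assessed systematically under toxicity aim 4.23

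*Combined protocol and SAP*

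**What the plan says.** **Schedule.** The EKG row of Table 2 (Section 11.0) has two marks, under Baseline and under the column headed 1 month Off Study. All cells from 2 weeks to 6 months are blank. The text above the table gives the purpose of the first tracing: "Baseline EKG to rule-out prolonged QTc, and if needed, echocardiogram, is required within 2 weeks of starting protocol therapy". During treatment, the footnote tells sites to "monitor for signs and symptoms of arrhythmia and for edema and fluid retention that may cause congestive heart failure", and then: "Obtain EKG/echocardiogram and cardiology consult as clinically indicated".

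**Timing of the last visit.** Section 6.0 calls it an off-therapy visit: "The 1 month, 3 month, 6 month, and 1-month off-therapy visits will consist of a comprehensive history and physical" exam. Section 14.0 sets the off-study point at: "Thirty days after the last dose of the investigational agent".

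**Pharmacokinetics.** Section 12.0, item 2: "The elimination half-lives of imatinib and its major active metabolite, the N-desmethyl derivative, are approximately 18 and 40 hours, respectively".

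**Aim and QT criteria.** Secondary aim 4.23 is: "To assess the tolerability and toxicity of imatinib in patients with sickle cell disease". Section 5.2.1 requires a corrected QT interval of at most 450 msec at entry. Section 5.2.2, item 10 begins: "Patients with a history of QT prolongation, need for concomitant use of anti-arrhythmics or other agents known to prolong QT interval". Item 11 excludes a family history of sudden cardiac death. The caption of Table 2 gives the purpose of its studies as confirming eligibility and following safety and efficacy on the drug.

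**Analysis.** Section 15.2 summarizes adverse events and laboratory data. Neither 15.2 nor 15.4 mentions EKG or QTc.

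**The concern.** The protocol takes QT seriously enough to limit it at entry and to exclude patients at raised risk, and it has a general aim of describing imatinib's toxicity in this disease. Yet the schedule takes no routine tracing while drug is present. The trial performs a follow-up EKG in every patient who reaches the final visit, but at a time when it cannot reflect exposure.

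What is at stake is information. An on-drug QTc change that reverses on stopping and causes no symptoms would leave no trace in the two routine EKGs. Section 8.0 counts any attributable Grade 3 or 4 non-hematologic toxicity as dose-limiting, with exceptions that do not include QTc, and those counts feed the stopping boundary in 15.3. A change that is never recorded cannot be counted there. Section 2.0 says the results will inform a later Phase II-B trial, and tracings not taken during treatment cannot be recovered afterwards.

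**Working it through.** The plan states no figure for this point, so there is none to reproduce.

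**Step 1: is the table row read correctly?** The text comes from a PDF, so a mark could have shifted. The EKG row has the full 10 cells (label plus nine visits). On the same grid, the physical-exam row falls at Baseline, Months 1, 3 and 6, and off study, and its follow-up marks match the full-examination visits in Section 6.0. A shifted mark is unlikely.

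**Step 2: how much drug is left at the follow-up EKG?** Inputs: half-lives of 18 h and 40 h (Section 12.0) and 30 days after the last dose (Sections 6.0 and 14.0). Half-lives elapsed k = days × 24 / half-life; fraction left = 0.5^k, assuming first-order elimination.

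| Days after last dose | Hours | Parent (18 h) | Metabolite (40 h) | Metabolite left |
|---|---|---|---|---|
| 23 | 552 | 552/18 = 30.7 | 552/40 = 13.8 | 7.0 × 10⁻⁵ (0.007%) |
| 30 | 720 | 720/18 = 40.0 | 720/40 = 18.0 | 3.8 × 10⁻⁶ |
| 37 | 888 | 888/18 = 49.3 | 888/40 = 22.2 | 2.1 × 10⁻⁷ |

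Days 23 and 37 assume that the 7-day visit window in Section 6.0 applies to this visit. At 30 days the parent fraction is 0.5^40 = 9.1 × 10⁻¹³.

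**Step 3: sensitivity.** If both half-lives were twice as long, 30 days would still be 720/36 = 20 parent and 720/80 = 9 metabolite half-lives, leaving 1/512, or about 0.2%, of the metabolite. If the column heading means one month after the off-study point and not after the last dose, the tracing is later still.

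**Step 4: what the routine pair can show.** Baseline is drug-free by design, and Step 2 shows that the follow-up is drug-free in effect. Their difference can reveal a persistent change only. As scheduled, 0 of the 20 treated patients have a routine on-drug QTc.

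**The case against.** The strongest reply is that the trial never undertakes to measure an effect on QTc. Aim 4.23 and the matching endpoint in 4.32 are general. No section names QTc as an endpoint or says that imatinib prolongs it. The QT criteria can be read as entry screens only. The on-treatment cardiac concerns that the plan spells out are arrhythmia symptoms, fluid retention and left ventricular dysfunction. An off-therapy tracing also has a use as an exit check. This stands in part: the relevance of QTc is an inference, and this is a design choice, not a flat contradiction. It does not explain why the table is captioned as following safety on the drug while its EKG row contains no on-drug tracing.

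A reader might go further and infer three things that the documents do not support:

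- **That the trial cannot assess QTc on drug at all.** EKGs and cardiology consults are allowed during treatment when clinically indicated. Patients have monthly visits, plus weekly calls or surveys in the first two months. An attributable Grade 3 or 4 QTc event found this way would count as dose-limiting. What is missing is systematic assessment: indication-driven tracings are selective and give no planned change from baseline.
- **That silent prolongation could never reach the adverse-event tables or the dose-limiting count.** It could, if an EKG happened to be taken for another reason.
- **That a planned paired comparison will give false reassurance.** No paired QTc analysis is planned. The risk arises only if someone later compares the two tracings and reads no change as evidence about the drug.

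**Conclusion.** The point holds in limited form. Both routine EKGs are effectively drug-free. The follow-up falls about 40 parent and 18 metabolite half-lives after the last dose, or about 14 metabolite half-lives if the visit is 7 days early. The trial therefore cannot systematically assess QTc on imatinib under aim 4.23, and asymptomatic on-drug prolongation would be missed unless a tracing were taken for some other reason.

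This rests on the half-lives in Section 12.0, first-order elimination, the row reading in Step 1, and the inference that QTc belongs under a general toxicity aim in a protocol that screens for it. The conclusion is insensitive to the visit window and survives a doubling of the half-lives. The primary endpoints are unaffected. This is an inexpensive improvement to the safety data. The QTc entry limit, the QT exclusions and the caption of Table 2 should be reconciled with its EKG row.

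**What to change.** 1. **Table 2:** move the one scheduled follow-up EKG from the off-therapy visit to an existing full physician visit during treatment, for example Month 1 or 3. Month 6 is less suitable because the last 30-day supply may have run out. At a visit 7 days late with no tablets left over, 168 h without drug is 168/18 = 9.3 parent and 168/40 = 4.2 metabolite half-lives.
2. **At that visit:** confirm from the journal, which records the date and time of each dose (Section 6.0), that the patient is still taking imatinib, and record the time since the last dose. Section 13.0 does not make compliance depend on completing the journal, so the site should also ask the patient directly. Time since dose matters because Section 12.0 puts peak concentration at 2 to 4 hours.
3. **Section 15.2:** add a descriptive summary of paired QTc change from baseline to that tracing, with the number of patients contributing.

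**Cost.** The number of scheduled EKGs is unchanged. The change needs a written amendment under Section 19.1.1, and IRB approval if it is judged to bear significantly on safety or scientific quality. The routine off-therapy exit tracing is lost. The summary will be crude: at most 20 patients, no control group, and a baseline capped at 450 msec, so regression to the mean could produce some apparent rise.

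Whether any off-therapy EKG is kept, and how a QTc result is handled, is for the investigators. If the schedule is not changed, Section 15.2 should state that the off-therapy EKG does not inform QTc on imatinib.
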